7.12 Data Safety Monitoring Plan

Medical Monitoring

It is the responsibility of the Principal Investigator to oversee the safety of the study at his/her site and communicate safety issues as per the monitoring plan. This safety monitoring will include careful assessment and appropriate reporting of adverse events as noted above, as well as the construction and implementation of a site data and safety-monitoring plan. Medical monitoring will include a regular assessment of the number and type of serious adverse events and a report to be submitted to the IRB. [name], MD is Director at Nathan Kline Institute, Marvin Stern Professor and Vice Chair for Research Department of Psychiatry

NYU Langone Medical Center. [name]. [name] is board certified in psychiatry and licensed to practice medicine in the state of New York.

Medical Monitor: [name] NYU United States (t) [contact] (f) [contact] [contact] http://psych.med.nyu.edu

7.13 Study Modification

Study modifications and specific recommendations for these protocol modifications, should they be necessary, will be elaborated, with accompanying rationale for each. This will be reported to sponsor, IRB, Medical Monitor and manufacturers who will donate the study drug (Shire Pharmaceuticals Group plc.).

After IRB approval the protocol, change will be communicated to the team at our weekly meeting. The protocol training for the change will be documented in the Protocol Training Logs. The change will be implemented as soon as possible.

7.14 Study Discontinuation

Stopping Rules

If subjects are experiencing a decline of 30% per the clinical assessments conducted, they will be withdrawn. Patient experiencing adverse events that, in the opinion of the investigator, the subject can no longer participate due to a change in medical status, experiences from adverse events, or patient becomes pregnant), the subject will be discontinued from the study. These are the possible reasons for termination from the study:

- Adverse events
- Lack of efficacy
- Lost to follow-up
- Pregnancy
- Withdrawal by subject
- Noncompliance
- Protocol violation
- Other

Documentation of study discontinuation will be added to subject source records. Withdrawal assessments will be conducted if investigator deems it is necessary. This will also be documented in the subject's source document folder..

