Our statistical analysis framework will be the general linear regression model. We will choose the distributional family and link function based on the distribution of the outcome variables. Each regression model will predict the outcome as the dependent variable with weeks in trial after the end of the two-week, single-blind, placebo lead-in as the independent variable. All analyses will use the ITT sample. For our design, a significant effect of week assesses the significance of the drug effect. We have chosen an IIT analyses as we can include all patients except for placebo responders in the analyses. We have chosen a single-blind placebo lead-in to define placebo responders, which are defined as patients who experience \geq 30% decrease in their total AISRS scores during placebo lead-in treatment. Placebo responders will be discontinued from the study. We anticipate that, based on the literature, 10% or fewer of patients will be placebo responders and that the overall discontinuation rate in the trial will be 20%. Changes within the day in TASS ratings 1 hour post dose vs. 4 hours post dose vs. 14-15 hours post dose will also be analyzed via the general linear regression model. Correlations between ADHD and executive function ratings will be examined via Spearman's correlation coefficients.

Statistical Power Analysis

Justification for sample size:

Up to 50 patients will be enrolled to be sure that 32 evaluable patients reach the end of treatment at week six. The graph shows power at different values of the Cohen's d effect size for estimating the difference between baseline and endpoint values. For our primary analysis, which uses a two-sided test with a type I error of 0.05, it shows that 32 evaluable patients, will give a power of 90% or more for effect sizes of 0.6 or greater. 0.6 is a reasonable expectation for an effect size: it is half of the 1.2 effect size reported by *Spencer et al. (2008)* and thus is at the lower end of what we should expect to see in this study.

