6.1.4 Blinding and Procedures for Unblinding

The study trial in regards to study drug is single blinded. The research staff, including study doctor, will know if the patient is receiving Mydayis or placebo. The subject will not know when they are on placebo or when they start the Mydayis treatment. The study pharmacist will know which study medication, either Mydayis or placebo, the patient is taking and can break the blind in case of an emergency.

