6.3.6 End of Study and Follow-up

Withdrawal/End of Treatment (Visit 7)

This hybrid visit will be conducted for subjects who have completed their treatment at Visit 7, subjects who wish early withdrawal or subjects whom the investigator deems participation is no longer effective or safe.

Participants will return to the study site for Visit 7 within 7 days of Visit 6. The following procedures and assessments will be performed at Visit 7: vital signs, AISRS, CGI-S, WebNeuro battery assessments (Verbal Interference/Stroop,Go/No-Go,CPT/TOVA), TASS, Expanded ASRS, C-SSRS and BRIEF-A.

Concomitant medications and AEs, if any, will be noted and drug accountability and compliance will be performed. Participants should report taking at least 80% of the prescribed study medication in order to be considered compliant.

The TASS will be done three times this day. The recommended dosing is at 5 am +/- 1 hour. The first TASS is done at half hour to one hour post dose (5:30 to 6 am +/- 1 hour), the second TASS is done 4 hours post dose (9am +/- 1 hour) and the third TASS is done 14-15 hours post dose (7pm+/- 1 hour).

Once all assessments and procedures for this visit are completed, participants will be given the Adult ADHD Referral list to help with the transitioning into treatment as usual.

Those that complete the study, and at the principal investigator's discretion, as a curtesy, can request and receive a letter stating their diagnosis and participation in the study.

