6.4.3 Planned Analyses

6.4.3.1 Primary Analyses

Our statistical analysis framework will be the general linear regression model. We will choose the distributional family and link function based on the distribution of the outcome variables. Each regression model will predict the outcome as the dependent variable with weeks in trial after the end of the single-blind placebo lead-in as the independent variable. All analyses will use the ITT sample. For our design, a significant effect of week assesses the significance of the drug effect. We have chosen an IIT analyses as we can include all patients except for placebo responders in the analyses. We have chosen a single-blind placebo lead-in to define placebo responders, which are defined as patients who experience \geq 30% decrease in their total AISRS scores during placebo lead-in treatment and will be discontinued from the protocol. We anticipate that, based on the literature, 10% or fewer of patients will be placebo responders and that the overall discontinuation rate in the trial will be 20% (*Manor et al. 2012*). The changes within the day in TASS ratings, 1-hour post dose vs. 4 hours post dose vs. 14-15 hours post dose will also be analyzed via the general linear regression model. Correlations between ADHD and executive function ratings will be examined via Spearman's correlation coefficients.

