6.4.5 Handling of Missing Data

Missing outcome data will be handled in regards to analysis in the following way: last observation will be carried forward.

7 - Trial Administration

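### Sections 6.3.6 and 7.14 contradict each other on whether early leavers are assessed, leaving chiefly their WebNeuro and BRIEF-A endpoints to the investigator's judgement

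*Combined protocol and SAP*

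**What the plan says.** **Section 6.3.6 (End of Study and Follow-up)** makes the visit part of the plan for leavers: "This hybrid visit will be conducted for subjects who have completed their treatment at Visit 7, subjects who wish early withdrawal". It also covers those whom the investigator takes out on grounds of efficacy or safety. The content is fixed: "The following procedures and assessments will be performed at Visit 7: vital signs, AISRS, CGI-S", followed by WebNeuro, TASS, Expanded ASRS, C-SSRS and BRIEF-A.

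**Section 7.14 (Study Discontinuation)** says otherwise: "Withdrawal assessments will be conducted if investigator deems it is necessary". It gives no criterion for when the assessments are needed.

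**Section 6.3 (Study Procedures)**, in the note after the follow-up call, names early withdrawal among the unscheduled visits that the principal investigator approves.

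Four other parts of the plan decide what this means for the analysis:

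- **Missing data (6.4.5):** "last observation will be carried forward".
- **Knowledge of treatment (6.1.4):** "The research staff, including study doctor, will know if the patient is receiving Mydayis or placebo".
- **Attrition:** Section 5.1 expects that "the overall discontinuation rate in the trial will be 20" per cent, and Section 6.4.3.1 that "10% or fewer of patients will be placebo responders". Responders are stopped at the end of the lead-in and left out of the analysis sample. Section 5.3 gives different numbers: 34 into the lead-in, 32 into treatment, 30-32 evaluable at the end.
- **Schedule (6.3, 6.3.5):** AISRS, CGI-S, TASS and Expanded ASRS are planned at every weekly treatment visit. WebNeuro and BRIEF-A are planned on treatment only at Visit 7, after a reading at the end of the lead-in.

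**The concern.** Site staff cannot tell from these sections whether a leaver must be assessed. If 7.14 governs, the decision rests with someone who has followed the patient's response, and Section 7.14 itself lists lack of efficacy and adverse events among the reasons for leaving. Collection of the endpoint could then depend on the endpoint.

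The design does little to absorb this. There is no concurrent control, and Section 6.4.3.1 reads the effect of week as the drug effect, so selective collection enters the estimate directly. Under carry-forward, holding or skipping the withdrawal visit determines which value stands as the patient's last.

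WebNeuro and BRIEF-A are most at stake. They carry secondary objectives 3 and 4, and executive function is also named in the primary objective. A leaver without a withdrawal assessment has no on-treatment value for either. For the weekly AISRS the stake is smaller.

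**Working it through.** **1. The plan's own figure.** The inputs are 32 evaluable patients, d = 0.6 and two-sided 0.05 (Section 6.4.2). A paired t-test by noncentral t gives power of 90.8%, and the normal approximation gives 92.4%. The stated 90% or more is reproduced. At the lower target of 30 patients, power is 88.8%.

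**2. Share of treated patients affected.** Let r be the share of placebo responders. If the overall 20% includes them, the share of treated patients who leave early is (0.20 - r)/(1 - r).

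| r | Share of treated patients | Leavers if 34 enter the lead-in |
|---|---|---|
| 0 | 0.20/1.00 = 20.0% | 34 x 0.20 = 6.8 |
| 5% | 0.15/0.95 = 15.8% | 34 x 0.15 = 5.1 |
| 10% | 0.10/0.90 = 11.1% | 34 x 0.10 = 3.4 |

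If the 20% excludes responders, the share is 20%. On Section 5.3 it is 32 - 32 = 0 to 32 - 30 = 2 patients, at most 2/32 = 6.25%.

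**3. Measures taken on treatment only at Visit 7.** The assumptions are mine: change has SD 1 and the same distribution in leavers and stayers, and an unassessed leaver is carried forward at zero change. Let m be the true mean change and q the share of leavers. The upper half of a normal distribution has mean m + 0.798.

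- No leaver assessed: mean = (1 - q)m.
- Only the better half assessed: mean = (1 - q)m + 0.5q(m + 0.798).
- Only the worse half assessed: mean = (1 - q)m + 0.5q(m - 0.798).

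| | q = 0.11 | q = 0.20 |
|---|---|---|
| m = 0.6, none assessed | 0.89 x 0.6 = 0.53 | 0.80 x 0.6 = 0.48 |
| m = 0.6, better half | 0.534 + 0.055 x 1.398 = 0.61 | 0.48 + 0.10 x 1.398 = 0.62 |
| m = 0.6, worse half | 0.534 - 0.055 x 0.198 = 0.52 | 0.48 - 0.10 x 0.198 = 0.46 |
| m = 0, better half | 0.055 x 0.798 = 0.04 | 0.10 x 0.798 = 0.08 |

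With no true change and n = 32, I simulated the extreme case in which a leaver is assessed only if improved (100,000 trials). Two-sided type I error is about 5.6% with 4 leavers and 7.0% with 6, against the nominal 5%.

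**4. AISRS.** A leaver seen at any treatment visit already has an on-treatment score, normally about a week old. The withdrawal visit decides only whether one more reading replaces it. The exception is a leaver who goes before Visit 4 and has no treatment score yet. The bias is q x f x g, where f is the share of leavers skipped and g the mean gap between the skipped and the carried score. The documents give neither f nor g, so no size follows.

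**The case against.** The strongest reply has four parts.

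- **Few patients are involved.** Placebo responders leave at a visit where the full battery is already scheduled, and they are not analysed. Section 5.3 leaves at most two treatment-phase leavers. Some leavers will be lost to follow-up and cannot be assessed under either rule. This stands, and it is why a range is given.
- **The primary measure is the least exposed.** This also stands, because AISRS is scheduled weekly.
- **Simple omission works against the drug.** For WebNeuro and BRIEF-A, skipping every leaver lowers the mean change. That is correct. Inflation needs selection on outcome, and even the extreme pattern moves type I error only to 5.6%-7.0%.
- **Knowledge of treatment adds little.** Section 6.1.3 has no random assignment and every treatment-phase patient receives Mydayis, so discretion cannot differ by arm. What matters is knowledge of response, which a clinician blinded to treatment would also have. I accept this; Section 6.1.4 is not the source of the problem.

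None of this reconciles the sections. The approval note in Section 6.3 does not settle which rule applies; it adds a further condition.

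**Conclusion.** The contradiction is real and needs correcting. It affects about 11% to 20% of treated patients on the plan's discontinuation figures, and 0 to 2 of 32 on Section 5.3. The main exposure is WebNeuro and BRIEF-A, and the direction of bias depends on who is skipped. The figures for those measures rest on the assumptions stated with them and illustrate size; they do not predict it.

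Three stronger readings are tempting, and the documents do not support them.

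- **A reader might infer that a fifth of patients are affected.** That is the top of the range. The 20% is an overall rate, given beside the placebo-responder figure, and on its natural reading includes responders.
- **A reader might infer that the AISRS change is overstated by 1 to 2 points.** This needs a 20% loss on treatment, every leaver skipped, and every skipped score 5 to 10 points worse than the carried one: 0.20 x 5 = 1.0 to 0.20 x 10 = 2.0. With the same assumed gap the range is 0.11 x 5 = 0.55 to 0.11 x 10 = 1.1 at 11%, and 2/32 x 5 = 0.3 to 2/32 x 10 = 0.6 for two leavers. The gap appears nowhere in the documents.
- **A reader might infer that the plan relies on a mixed model that cannot repair the loss.** The plan specifies general linear regression with carry-forward. A mixed model could accommodate decisions based on recorded weekly scores; it would fail if they followed unrecorded deterioration.

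**What to change.** Reconcile Section 7.14 and the note in Section 6.3 with Section 6.3.6, so that efficacy assessments at withdrawal follow one rule that does not depend on the investigator's view of response:

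- Collect AISRS, CGI-S, TASS, Expanded ASRS, WebNeuro and BRIEF-A from every leaver who agrees.
- Record the date and reason for leaving and, where an assessment is not obtained, why not.
- State in Section 6.4.5 that a withdrawal score enters the regression at its actual week, and that any carry-forward starts from it.

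The visit is already described in Section 6.3.6, so the change is a few sentences of text and a few extra assessment visits. It concerns data collection only. The rules for stopping treatment and the safety checks at withdrawal are not addressed here.

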7.15 Study Completion

18 months after start of recruitment

7.16 Conflict of Interest Policy

All study members will complete the NYU financial disclosure forms. [name], who has a conflict of interest with this study (patent ownership, royalties, or financial gain greater than the minimum allowable by their institution, etc.) had the conflict reviewed by a properly constituted Conflict of Interest Committee with a Committee sanctioned conflict management plan that has been reviewed and approved by the study sponsor prior to participation in this study. All NYULMC investigators will follow the applicable University conflict of interest policies.

7.18 Publication Plan

The investigator at NYU will have the primary responsibility for publishing the study results. The data will be analyzed and discussed prior to submission of the study results for publication.

Neither the complete nor any part of the results of the study carried out under this protocol, nor any of the information provided by the sponsor for the purposes of performing the study, will be published or passed on to any third party without the consent of the study investigator of this study.

Appendices

Appendix #	Title	Section	Торіс
1		Synopsis	Visit Schedule Table (Optional)
2		Synopsis	Study Flow Chart (optional)
3		2 Background	2.1.1 Preclinical Experience
4	FDA 2017 Reference ID: 4114154 Medication guide	2 Background	2.1.1 Preclinical Experience
5		6 Methods	6.1.1 Identity of Investigational Product/New Drug
6		6 Methods	6.1.1 Identity of Investigational Product/New Drug
7		6 Methods	6.1.6 Storage Conditions
8	ICF Progress Note Template	6 Methods	6.3.2 Informed Consent

August 12, 2021 version

9	InformedConsentProcessandDocumentation	6 Methods	6.3.2 Informed Consent
10	ICF	6 Methods	6.3.2 Informed Consent
11	Pregnant Partner Contact Sheet (Version: 09/08/2014)	6 Methods	6.3.2 Informed Consent
12	Pregnant Partner Information Release Form	6 Methods	6.3.2 Informed Consent
13	schedule of events and providers	6 Methods	6.3.3 Screening
14	Phone_Screen	6 Methods	6.3.4 Recruitment, Enrollment and Retention
15	Phone _Script_Verbal_Consent	6 Methods	6.3.4 Recruitment, Enrollment and Retention
16	follow up letter	6 Methods	6.3.7 Removal of subjects
17	Statistical-Analysis- Plan	6 Methods	6.4.1 Statistical Design

18	medical	monitoring	7 Trial	7.12 Data Safety	
	plan		Administration	Monitoring Plan	

References

- Adler, L. A., Faraone, S. V., Spencer, T. J., Berglund, P., Alperin, S., & Kessler, R. C. (2017). The structure of adult ADHD. International journal of methods in psychiatric research, 26(1), e1555.
- Adler, L. A., & Gorny, S. W. (2019). Pilot Study of Droxidopa With Carbidopa in Adults With ADHD. J Atten Disord, 23(2), 189-198. doi:10.1177/1087054715580393
- Adler, L. A., Shaw, D. M., Spencer, T. J., Newcorn, J. H., Sitt, D. J., Morrill, M., . . .
 Faraone, S. V. (2011). Reliability and validity of the Time-Sensitive ADHD
